Shown are three response to a 5s current injection in a single motor neuron from a septic rat before and at two times after injection of 3 mg/kg lorcaserin. Before lorcaserin, the motor neuron fires action potentials only infrequently during the 5s current injection. 15 minutes after lorcaserin, the motor neuron fires the whole 5s, but firing is still slow and somewhat inconsistent. 1 hour after injection of lorcaserin, the motor neuron fires normally for the whole 5 s.

known that activation of serotonin receptors (5-HT_{2C}) in the spinal cord increases persistent inward sodium current to allow motor neurons to fire repetitively(15-18). Based on this knowledge, rats that had been septic for 1 day were treated with 3 mg/kg of the selective 5-HT_{2C} agonist lorcaserin. **lorcaserin (trade name Belviq) has an excellent safety profile and is FDA-approved for weight loss(19).** Using glass microelectrode impalements of single motor neurons for up to 2 hours, the firing pattern before and after intraperitoneal injection of lorcaserin in 4 different rats were recorded (one motor neuron studied per rat; Figure 2). Prior to injection of lorcaserin, motor neurons were unable to sustain steady firing (top trace Fig 2). Fifteen minutes after lorcaserin, motor neuron firing was improved, but still not normal (middle trace Fig 2). One hour after injection of lorcaserin, motor neurons fired normally throughout the 5 second current injection (lower trace Fig 2). There was similar normalization of firing in all 4 motor neurons that recorded before and after lorcaserin injection.

3-e) Drug dosing

The lorcaserin dose that normalizes motor neuron firing in rats is 3 mg/kg delivered via intraperitoneal injection. The human dose for weight loss is 10 mg PO twice daily, but doses up to 60 mg were tolerated in clinical trials. Based on rat-to-human allometric scaling of both pharmacokinetic parameters and 5-HT_{2C} receptor sensitivity (EC₅₀), the 3 mg/kg dose in a rat that fully restored motor unit function is 0.26 mg/kg or 18 mg in a 70 kg adult. Based on doses of lorcaserin that were given to patients prior to FDA approval and rat to human allometric scaling, it appears that treatment of patients with effective doses of lorcaserin is feasible.

3-f) Study Design Rationale

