On Day 4, the intervention and control group participants will not receive any lorcaserin/placebo, but will undergo assessments (identical to Day 2).

4-a-6) Measurements

Participants will be monitored to ensure safety of lorcaserin/placebo administration. This monitoring will include a daily review of interim history (via chart review), medications, and laboratory values (details below), as well as assessment for changes in mental status and monitoring for serotonin syndrome (see table 3).

We also will obtain a battery of outcome measures to test the efficacy in improving muscle strength and assess the safety of lorcaserin, as described in tables 3.

All monitoring will be done by assessors blinded to group allocation.

Table 3: Safety and Efficacy Measures (numbers indicate the number of times within each study day that each measurement is performed)

Measurement	Number of assessments			
	Day 1*	Day 2†	Day 3***‡	Day 4†
Safety Measures				
Chart Review	1	1	1	1
Laboratory Tests (details below)	1	1	1	1
EKG	2	1	1	1
RASS sedation score	2***	1	2***	1
CAM-ICU delirium screen	2***	1	2***	1
Neuro Psychiatric Screen	2	1	1	1
Hunter Serotonin Toxicity Criteria	1	1	1	1

Efficacy Measures				
Handgrip Strength (Primary Outcome)	2***	1	2***	1
Arm & leg strength (MMT using MRC Scale)	2***	1	2***	1
Quadriceps Strength using handheld dynamometry	2***	1	2***	1
Lorcaserin serum drug levels [‡]	1	1	1	1
Electromyography & Nerve Conduction Study	once only to assess for any peripheral neuromyopathy****			

MMT: Manual muscle strength testing; MRC: Medical Research Council; HHD: Hand-Held Dynamometry; EKG: Electrocardiogram; RASS: Richmond Agitation Sedation Scale; NPI-C: Neuropsychiatric Inventory - Clinician Rating Scale; CAM-ICU: Confusion Assessment Method for the ICU; Hunter Criteria: will be used to evaluate patients for serotonin syndrome (24)

* 10 mg of lorcaserin or placebo administered

** 30 mg of lorcaserin or placebo administered

*** measures are performed as close to the time as drug or placebo administration as possible (within 4 hours) and as soon as possible (between 2 - 6 hours) after drug or placebo administration, on Days 1 and 3 only

**** EMG & NCS will be performed at any time point after the patient is randomized into study, and will be used to help interpret the results of strength tests

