4-a-6.5) Confusion Assessment Method for the Intensive Care Unit (CAM-ICU): The CAM-ICU is a validated delirium screening test for ICU patients. Participants will be screened for their delirium status daily as well as pre- and post- drug or placebo administration as indicated in table 3above.

4-a-6.6) Neuropsychiatric Screening adapted from NPI-C (Neuropsychiatric Inventory-Clinician Rating Scale): NPI-C is a validated instrument used to screen for the presence and severity of symptoms in a number of psychiatric domains, in non-verbal patients, and includes clinician-rating methodology in addition to patient and caregiver inputs(26). Subscales of NPI-C will be adapted to perform daily screening for any hallucinations, delusions, euphoria and agitation in study participants.

4-a-6.7) Hunter Serotonin Toxicity Criteria: Daily physical examinations for serotonin toxicity criteria will be performed using this pre-existing criteria(24) as indicated in table 3 above.

Efficacy Measures

4-a-6.8) Dynamometry of Handgrip Strength (Primary Outcome): Bilateral handgrip strength will be measured pre- and post-drug or placebo administration at time points listed in table 3 above, using a Jamar Plus digital dynamometer in sitting position(27;28)

4-a-6.9) Manual Muscle Strength Testing: Standardized manual muscle testing (MMT) of patients' arm and leg strength using the Medical Research Council (MRC) scale will be measured pre- and post-drug or placebo administration in table 3 above, via physical examination.

4-a-6.10) Dynamometry of Quadriceps Strength: Bilateral quadriceps muscles strength will be measured using a Micro FET Dynamometer in supine position(27;28) pre- and post-drug or placebo administration as indicated in table 3 above. If the patient cannot or will not perform the test for an individual muscle group, the reason for this will be recorded.

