4-a-6.11) Serum Drug Levels: Daily blood samples will be collected to determine lorcaserin serum levels by a LC-MS/MS assay and pharmacokinetics. The serum drug samples will be collected and run in at least 2 batches, with the first batch run on specimens after randomization of at least the first 3 patients to lorcaserin (will be done without unblinding the research team regarding the study ID of these subjects). The peak plasma concentration after oral dosing is 1.5 to 2 hours. However, feeding can increase the peak plasma time by 1 hour. Thus, peak concentration samples will be collected at 2hours \pm 15 minutes for NPO patients and at 3 hours \pm 15 minutes for fed patients. Lorcaserin has a plasma half-life of about 11 hours, and trough concentration samples will be collected at approximately two half-lives, or 24 hours \pm 30 minutes.

4-a-6.12) Electromyography (EMG) and Nerve Conduction Studies (NCS):

Nerve conduction will be assessed via the following screening nerve conduction studies in participants after enrolment, to detect potential peripheral neuropathy. NCS results will help us interpret the results of strength tests.

- Motor NCS of bilateral peroneal nerves
- Motor NCS of unilateral ulnar nerve. If ulnar neuropathy at the elbow is diagnosed (slowing of ulnar conduction velocity across the elbow to below 35 m/s or a drop in ulnar motor amplitude of >50% with stimulation above the elbow), Motor NCS of the ulnar nerve of the other extremity will be performed as well.

- Sensory NCS of unilateral ulnar and sural nerves

Motor unit recruitment rate will be assessed via the following EMG studies as well

- EMG of unilateral vastus lateralis muscle
- EMG of unilateral deltoid muscle

If EMG and NCS studies have already been done for clinical purposes, they will NOT be repeated for research purposes, and the pre-existing results will be used for research purposes.

4-b) Study duration and number of study visits required of research participants.

Each participant regardless of group, will be in the study for two 2-day blocks. The detailed timeline of events are detailed in Table 3.

4-c) Blinding, including justification for blinding or not blinding the trial, if applicable.

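### The post-dose grip test opens at 2 h for every patient, although the plan puts the fed peak at 2.5 to 3 h and moves only the blood sample, not the primary outcome

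*Combined protocol and SAP*

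**What the plan says.** Table 3 (section 4-a-6) marks handgrip, manual muscle testing and quadriceps dynamometry with the three-asterisk footnote. That footnote places the post-dose assessment "as soon as possible (between 2 - 6 hours) after drug or placebo administration, on Days 1 and 3 only". Section 4-a-6.8 adds no timing of its own: "Bilateral handgrip strength will be measured pre- and post-drug or placebo administration at time points listed in table 3 above".

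Section 4-a-6.11 treats the blood sample differently. It states "The peak plasma concentration after oral dosing is 1.5 to 2 hours" and then "However, feeding can increase the peak plasma time by 1 hour". For that reason the peak sample is split by feeding status: 2 h for NPO patients and 3 h for fed patients, each within 15 minutes. It also states "Lorcaserin has a plasma half-life of about 11 hours".

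Section 7-a makes the same-day change in grip after 30 mg, against control, the primary comparison. Section 7-b repeats it for 10 mg and adds a pooled Emax analysis of drug concentration against strength. No section ties the grip test to the serum sample or delays it in fed patients.

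**The concern.** The plan regards food as important enough to move the blood sample but leaves the primary outcome on a common start time. The window alone would matter little. The instruction to test as early as possible is what steers staff to the 2 h end, which in a fed patient lies before the plan's own peak.

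Three things follow. Lorcaserin patients who are fed may be tested while the level is still rising. Placebo patients have no drug effect to lose, so any shortfall falls on the treatment difference. Fed and NPO patients would be tested at different points on the curve within an arm of only 10. And a fed patient's grip may be recorded well before the serum sample it is to be paired with in the Emax model. The 10 mg comparison is exposed in the same way.

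**Working it through.** **1. Fed peak, from the plan's figures.** Oral peak 1.5 to 2 h plus 1 h for feeding = 2.5 to 3 h. The 3 h fed sample is the upper end of this range, just as the 2 h NPO sample is the upper end of 1.5 to 2 h, so the plan's sampling times are reproduced. A fed patient tested at 2 h is 0.5 to 1 h before peak and 1 h before the nominal sample (45 to 75 minutes, given the 15-minute tolerance). Of the 4 h window, 0.5/4 = 12.5% to 1/4 = 25% lies before the fed peak.

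**2. The plan's sample-size statement (section 7-c).** Inputs: 10 and 5 patients, baseline SD 9 kg, r = 0.8, alpha 0.05 (taken as two-sided; the plan does not say).

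- SD of change = 9 × √(2 × (1 − 0.8)) = 5.69 kg
- Standard error = 5.69 × √(1/10 + 1/5) = 3.12 kg
- Detectable difference at 80% power, normal approximation = (1.960 + 0.842) × 3.12 = 8.73 kg, consistent with the stated figure of just over 9 kg
- Power at 9 kg for the planned t-test (noncentral t, 13 df, noncentrality 9/3.12 = 2.89) = 76%. This is the reference value below.

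**3. Level at 2 h and 3 h in a fed patient.** Assumed model: one compartment, first-order absorption, level proportional to exp(−ke·t) − exp(−ka·t). The 11 h half-life gives ke = ln 2/11 = 0.0630 per h. ka is solved from peak time = ln(ka/ke)/(ka − ke). The food effect is represented in two ways: slower absorption, or a 1 h lag before absorption at the NPO rate.

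**4. Power if the effect is proportional to level.** The 9 kg effect is multiplied by the level at 2 h as a share of peak. *All fed* means every lorcaserin patient is fed and tested at exactly 2 h. *Half fed* applies the loss to half the arm and leaves the others at full effect.

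| Food effect | Fed peak | ka (per h) | Level at 2 h | Level at 3 h | Effect at 2 h | Power, all fed | Power, half fed |
|---|---|---|---|---|---|---|---|
| Slower absorption | 2.5 h | 1.262 | 98.7% | 99.2% | 8.9 kg | 75% | 76% |
| Slower absorption | 3 h | 0.977 | 95.5% | 100% | 8.6 kg | 72% | 74% |
| 1 h lag | 2.5 h | 2.523 | 96.8% | 98.7% | 8.7 kg | 73% | 75% |
| 1 h lag | 3 h | 1.715 | 89.4% | 100% | 8.0 kg | 67% | 71% |

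For comparison, an NPO patient at 2 h is at 98.7 to 100% of peak. In all four fed cases 3 h is better than 2 h.

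**5. If the effect saturates.** Take effect proportional to D/(D + EC50), with D the 30 mg dose scaled by level and EC50 expressed as an equivalent dose. The plan gives no EC50; 9 and 18 mg are illustrations. In the worst row (89.4%, equivalent to 26.8 mg), the share of effect kept is (26.8/35.8)/(30/39) = 0.973 for 9 mg and (26.8/44.8)/(30/48) = 0.957 for 18 mg. Power is then 74% and 72%.

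**6. The other end of the window.** At 6 h the modelled level is 82 to 88% of peak in fed patients and 77 to 81% in NPO patients.

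**The case against.** The strongest reply is that the loss is small and the early instruction has its own merit. On the plan's figures the fed level at 2 h is already within about 11% of peak, and by 2.5 h it is at least 98%. The plan's Emax model saturates, and the primary comparison uses 30 mg, while the rat dose that restored firing is scaled to 18 mg in a 70 kg adult; 89% of 30 mg is about 27 mg. A test at 6 h generally gives up more exposure than a fed test at 2 h. Early testing also shortens the time in which sedation could end a patient's testing under section 4-f item 4. And the trial is a convenience-sample pilot. All of this stands on size. None of it removes the mismatch, since the footnote already steers testing away from the 6 h end and no other text aligns grip with the fed peak.

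A reader might infer something stronger: that the effect lags the plasma level, so a fed patient at 2 h shows well short of the full effect. The rat account, "Fifteen minutes after lorcaserin, motor neuron firing was improved, but still not normal", with normal firing at 1 hour, invites this. With an assumed 15-minute effect-site half-time, the fed effect at 2 h would be 0.70 to 0.94 of maximum, and power could fall to 47%. The documents do not support those figures. The rat traces follow intraperitoneal injection and come without plasma levels, so the build-up may be absorption alone, and they give no human delay. The 47% also needs the pure lag, the 3 h peak, every patient fed, every test at exactly 2 h, and a linear effect, all together. A delay is possible and would enlarge the loss, but its size cannot be taken from the plan.

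**Conclusion.** The mismatch is real and the consequence modest. Followed as written, the footnote allows the primary outcome in a fed patient to be measured 0.5 to 1 h before the peak implied by section 4-a-6.11 and about 1 h before the serum sample.

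The fed level at 2 h is 89 to 99% of peak, against 99 to 100% at 3 h. Power at 9 kg is 67 to 75% instead of 76% in the worst case. The loss is smaller if fewer patients are fed (the plan gives no share), if testing in practice falls later than 2 h, or if the effect is near saturation at 30 mg. These figures rest on the one-compartment model, the two representations of the food effect, proportionality of effect to level, and the plan's SD and correlation. The timing mismatch itself rests on none of them, and neither does the mispairing of grip and serum level in the Emax analysis. It would be wrong to conclude that the primary comparison is invalidated or that a large share of the effect is missed.

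**What to change.** Amend the three-asterisk footnote so that the post-dose strength tests follow the split already used for the peak sample: earliest 2 h if NPO, earliest 3 h if fed. Start the tests straight after that patient's peak sample and keep the 6 h limit for both groups. Record feeding status at dosing and the actual times of dose, sample and grip test. This also brings grip and serum level together for the Emax analysis.

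The cost is one footnote and a few recorded fields, with no added visit or sample. There are downsides. Fed patients are tested up to 1 h later and have a 3 h rather than a 4 h window. There is slightly more chance of intervening sedation under section 4-f item 4. The blinded strength assessor must be scheduled to the peak draw; section 8-a lets clinical staff take blood, so the assessor would not otherwise have to be there. The change does not address the lower exposure at the 6 h end, though recording test times would allow it to be examined.

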a) Serotonin Syndrome or Neuroleptic Malignant Syndrome (NMS) like Reactions: Although lorcaserin has not been associated with any known cases of either serotonin syndrome or NMS, the safety of co-administration of lorcaserin with other serotonergic or anti-dopaminergic agents has not been established.

b) Cardiac valvular and conduction abnormalities: Asymptomatic aortic or mitral regurgitations were seen in patients who were in a randomized control trial of lorcaserin vs placebo for a one-year period, likely due to long-term activation of serotonin receptors on cardiac interstitial cells. In a similar year-long trial of lorcaserin vs placebo, some patients experienced a decrease in their heart rate over time.

c) Cognitive Impairment and Depression or suicidal thoughts: in trials of at least 1 year duration, lorcaserin administration was associated with difficulty with concentration and attention, difficulty with memory and confusion, and some mood problems such as depression.

d) Psychiatric Disorders (including euphoria and dissociation): have been associated with short-term studies of lorcaserin at supratherapeutic dosages.

e) Hypoglycemia was observed in some participants with Type 2 Diabetes on lorcaserin while concomitantly on a sulfonylurea.

f) Priapism: Although lorcaserin has not been associated with cases of priapism, serotonergic drugs like lorcaserin have been associated with priapism.

2) Risk of stopping/adjusting other medications: There may be risks associated with the temporary stopping of other medications

3) EMG and Nerve Conduction Studies: Participants may experience some discomfort. There might also be some bruising in the area where the wire is inserted. Most subjects will not experience any bleeding with the needle studies; even for patients receiving therapeutic anticoagulation, the reported risk of clinically silent hematoma formation is less than 2% (30). If bleeding occurs, no more than a few drops is expected. The risk of infection is extremely small.

4) Blood sampling: Participants may experience discomfort, bruising or bleeding at the site of blood draws. All patients will have blood drawn for research purposes either through indwelling catheters or percutaneously by either a licensed clinical staff or trained research personnel. Risks of percutaneous blood draws are uncommon and include bleeding, discomfort and bruising.

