5) Chart Abstraction: There is a risk of loss of privacy, since we will be collected data on participants.

6) Strength testing: Participants may feel some tiredness or discomfort in the arm and leg muscles

7) Questions: There is a small chance that a participant could become uncomfortable, bored or fatigued in answering our questions.

8-b) Steps taken to minimize the risks.

1) Side effects of drug/placebo

a) Serotonin Syndrome and NMS-like reactions:

Although this syndrome is rare, the theoretical risk of serotonin syndrome and NMS-like reactions will be mitigated by

- i. Monitoring participants for liver and renal failure, which may affect drug levels
- ii. Reviewing medication lists to exclude patients on drugs that may cause serotonin syndrome when administered along with lorcaserin (see Appendix A and section 4-d above).
- iii. Allowing participants to be on no more than 1 serotonergic agent (plus lorcaserin/placebo) during the trial.
- iv. Closely monitoring patients, for toxicity using the NPI-C for mental status changes and Hunter Criteria for Serotonin toxicity.

b) Cardiac valvular and conduction abnormalities:

Patients with a history of valvular heart disease, bradycardia, and 2nd or 3rd degree AV block without pacemaker will be excluded. Participants are unlikely to develop new onset valvular defects given that they will only receive two doses in this trial. Participants will be closely monitored via EKG for bradycardia and new onset 2nd or 3rd degree AV block.

c) Cognitive impairment, Psychiatric Disorders (including euphoria and dissociation) and Depression:

Patients with pre-existing cognitive impairment and psychosis will be excluded. During the trial, patients will be closely monitored using the RASS, CAM-ICU and NPS (Neuropsychiatric screening) instruments.

d) Hypoglycemia: Patients will be excluded if they are receiving a sulfonylurea medication at the time of the study

e) Priapism: this is a theoretical risk will be mitigated by excluding patients with a prior history of priapism, and monitoring during the trial via any noted side effect.

2) Risks of stopping/adjusting other medications: These risks will be assessed on a case-by-case basis, in consultation with the participants' medical team.

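### Section 8-b says dissociation is closely monitored, but none of the three instruments it names is described as assessing dissociation

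*Combined protocol and SAP*

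**What the plan says.** Section 8-a item 1d names the risk: "Psychiatric Disorders (including euphoria and dissociation): have been associated with short-term studies of lorcaserin at supratherapeutic dosages". Section 8-b item 1c takes it up under the heading "Cognitive impairment, Psychiatric Disorders (including euphoria and dissociation) and Depression" and states the safeguard: "During the trial, patients will be closely monitored using the RASS, CAM-ICU and NPS (Neuropsychiatric screening) instruments".

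Sections 4-a-6.4 to 4-a-6.6 describe the three instruments. The RASS is a measure of agitation and sedation. The CAM-ICU is a screen for delirium. For the neuropsychiatric screen, section 4-a-6.6 says: "Subscales of NPI-C will be adapted to perform daily screening for any hallucinations, delusions, euphoria and agitation in study participants". Table 3 schedules that screen twice on Day 1 and once on each of Days 2, 3 and 4.

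Depression has a different basis. Section 8-a item 1c says "in trials of at least 1 year duration, lorcaserin administration was associated with difficulty with concentration and attention", and the same sentence goes on to mood problems such as depression.

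On dose, section 4-a-5 gives 10 mg on Day 1 and 30 mg on Day 3. Section 3-e gives 10 mg twice daily as the weight-loss dose and reports that up to 60 mg was tolerated in clinical trials.

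**The concern.** The protocol names two psychiatric effects in one sentence and promises instrument-based monitoring for both. Only one of them, euphoria, appears in the description of the screen. This is a mismatch between a stated safeguard and the measurement described to deliver it.

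It matters because safety in ICU patients is objective 2-1, and the protocol says the drug has not been used in that population. Section 4-e counts subjective assessments of cognitive and psychological symptoms among the outcomes, and uses them to justify the blinded placebo group. Section 9-a looks ahead to repeat-dosing studies if the results are encouraging. If staff follow the plan as written, nobody is asked to look for dissociation in a structured way. A table with no cases would then be uninformative, and later readers could take it as reassurance.

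**Working it through.** No sample-size or error-rate figure underlies this point, so the check is a cross-match of sections, with one small dose comparison.

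**Step 1. Effects listed, monitoring claimed, content described.**

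| Effect | Listed in 8-a | Named in 8-b item 1c | RASS (4-a-6.4) | CAM-ICU (4-a-6.5) | Neuropsychiatric screen (4-a-6.6) |
|---|---|---|---|---|---|
| Euphoria | 1d, short-term studies | Yes | No | No | Yes |
| Dissociation | 1d, short-term studies | Yes | No | No | No |
| Depression | 1c, trials of at least 1 year | Yes | No | No | No |

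For dissociation, 0 of the 3 assigned instruments is described as covering it. Of the two effects named in item 1d, 1 of 2 is covered.

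**Step 2. Could another scheduled measure fill the gap?** The remaining safety rows of Table 3 are chart review, laboratory tests, EKG and the Hunter criteria. None is described as assessing dissociation. The treatment-discontinuation list in section 4-f mentions psychosis, hallucinations and euphoria, so it does not supply the missing domain either.

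**Step 3. Did the plan intend passive capture?** For priapism, section 8-b item 1e says openly that monitoring relies on any side effect noted. Item 1c makes a different claim: close monitoring with named instruments. Passive capture may also be filtered. Section 8-c treats agitation and delirium as anticipated events that are not reportable unless judged to be associated with the protocol. A dissociative episode charted as delirium could be lost that way.

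**Step 4. Is an effect of supratherapeutic dosages relevant here?** The weight-loss regimen is 10 mg twice daily, so the daily total is 2 × 10 = 20 mg. The Day 3 dose is 30 mg in one administration: 30/10 = 3 times the single dose and 30/20 = 1.5 times the daily total. It exceeds both. The documents do not say at what dose dissociation was seen, so this shows relevance and not an expected rate.

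**The case against.** The strongest reply is that the plan is not blind to psychiatric events. Chart review is daily and looks for any safety issue. Section 4-a-6 includes assessment for changes in mental status, and section 8-b item 1a uses the NPI-C for that purpose. Section 8-c provides a case report form for clinically important unanticipated problems and study-related serious events. A reader might infer from the cross-match that dissociation is not captured at all; these provisions show that to be too strong. They do leave it without a dedicated, structured assessment.

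Second, section 8-b item 1c names the three instruments jointly under a grouped heading and does not assign dissociation to the neuropsychiatric screen in particular. That is correct, but it does not help, because neither of the other two is described as covering dissociation. The adapted form itself is not in the documents, so the absence of an item is inferred from the domain list in section 4-a-6.6. If the form already has one, that section should say so.

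Third, a reader might give depression equal weight. Section 8-a item 1c ties it to trials of at least 1 year, whereas this trial gives two single doses with assessments through the day after the second. The wording gap is real, but it matters less.

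Fourth, a reader might suppose that participants are too sedated or uncommunicative to report symptoms. The inclusion criteria require that they obey commands. Some may be delirious, and an added item would give some false positives in them. The placebo arm and a pre-dose answer help with interpretation.

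Finally, section 7 plans no analysis of dissociation, so no planned comparison changes. The documents also give no incidence. Any assumed rate would describe how often events occur, not how many the plan would miss.

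**Conclusion.** The point holds for dissociation. The protocol claims close monitoring of an effect that none of the three instruments it names is described as measuring. The size is best stated as a coverage count: 0 of 3 assigned instruments, and one of the two effects in section 8-a item 1d left without structured ascertainment in either arm. No number of missed events can be given.

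The conclusion rests on two things: that the four domains in section 4-a-6.6 are the full content of the adapted screen, and that an effect reported at supratherapeutic dosages is relevant at 30 mg. The documents make the second plausible without settling it. The consequence is limited to interpretation of safety: finding no reported dissociation would not show that it did not occur. The grip-strength analysis is unaffected. The change is worth making because safety is the first objective and the remedy is small.

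**What to change.** In section 4-a-6.6 and the neuropsychiatric screen row of Table 3, add one fixed item for dissociation with a yes/no answer. Ask it in both arms at the screen's existing time points, specify that one of the two Day 1 assessments is before dosing so that there is a baseline, and report the answers by arm. Table 3 does not say when the single Day 3 screen falls relative to dosing, so that should be stated at the same time.

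If the item is not added, amend section 8-b item 1c so that it no longer claims dissociation is monitored, and draw no safety conclusion about it. For depression, a wording correction in section 8-b is enough.

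The cost is about a minute per assessment. With 2 + 1 + 1 + 1 = 5 screens per participant and 15 participants, that is at most 5 × 15 = 75 screens, or roughly 75 minutes over the whole trial, plus some false positives in delirious patients. Neither option alters dosing, the discontinuation criteria or the sample size.
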